5.1.2 Exclusion Criteria

- 1) Less than 21 days since the last dose of intravenous anticancer chemotherapy or less than five half-lives from a small molecule targeted therapy or oral anticancer chemotherapy before the first IMP administration
- 2) Any immunotherapy within preceding 6 weeks from the first IMP administration
- 3) Investigational therapy or major surgery within 4 weeks before the first IMP administration
- 4) Active clinically serious infection > Grade 2 NCI-CTCAE version 5.0 ([Appendix 5 - Common Toxicity Criteria Gradings](#)) within preceding 2 weeks before the first IMP administration
- 5) Brain metastases
- 6) Subject has not recovered from the previous therapies to Grade ≤ 1 severity as classified by the NCI-CTCAE version 5.0 (except Grade ≤ 2 alopecia, neuropathy or thyroid disorders)
- 7) Pregnant or lactating women
- 8) History of second malignancy except for non-melanotic skin cancer, cervical carcinoma in situ or superficial bladder cancer, or any other malignancy treated previously with curative intent and more than three years without relapse
- 9) Evidence of severe or uncontrolled systemic diseases, congestive cardiac failure New York Heart Association (NYHA) class ≥ 2 ([Appendix 7 - NYHA classification](#)), Myocardial Infarction (MI) within 6 months or laboratory finding that in the view of the investigator makes it undesirable for the subject to participate in the trial
- 10) Any medical condition that the Investigator considers significant to compromise the safety of the subject or that impairs the interpretation of IMP toxicity assessment
- 11) Confirmed human immunodeficiency virus infection
- 12) Symptomatic cytomegalovirus infection
- 13) Subjects with active auto-immune disorder (except type I diabetes, celiac disease, hypothyroidism requiring only hormone replacement, vitiligo, psoriasis, or alopecia)
- 14) The subject requires systemic corticosteroid or other immunosuppressive treatment
- 15) Subjects with organ transplants
- 16) Subjects in dialysis
- 17) Use of Live (attenuated) vaccines for 30 days prior to the start of study treatment, during treatment, and until last visit
- 18) Subject is unwilling or unable to comply with treatment and trial instructions
- 19) Subjects with known hypersensitivity to the IMP or any of the pharmaceutical ingredients

5.1.3 Specific Additional Exclusion Criteria for HCC

- 1) Any ablative therapy (Radio Frequency Ablation or Percutaneous Ethanol Injection) for HCC (this should not exclude subjects if target lesion(s) have not been treated and occurred > 6 weeks prior trial entry)
- 2) Hepatic encephalopathy
- 3) Ascites refractory to diuretic therapy
- 4) Child-Pugh score ≥ 7

6 SCREENING AND CONSENT

6.1 Informed Consent

It is the responsibility of the Investigator to obtain a written informed consent from each subject prior to performing any trial related procedure. A Patient Information and Consent Document is provided to facilitate this process. Investigators must ensure that they adequately explain the aim, trial treatment, anticipated benefits and potential hazards of taking part in the trial to the subject. The Investigator should also stress that the subject is completely free to refuse to take part or withdraw from the trial at any time. The subject should be given ample time (e.g. 24 hours) to read the Patient Information and Consent Document and to discuss their participation with others outside of the site research team. The subject must be given an opportunity to ask questions which should be answered to their satisfaction. The right of the subject to refuse to participate in the trial without giving a reason must be respected.

If the subject expresses an interest in participating in the trial, they should be asked to sign and date the latest version of the Patient Information and Consent Document. The Investigator must then sign and date the form. A copy of the Patient Information and Consent Document should be given to the subject, a copy should be filed in the hospital notes, and/or in the Investigator Site File (ISF). Once the subject is entered into the trial, the subject's trial number should be entered on the Information and Consent Document maintained in the ISF.

Details of the informed consent discussions should be recorded in the subject's medical notes; this should include the date consent was given and the short name of the trial or protocol code. Throughout the trial, the subject should have the opportunity to ask questions about the trial and any new information that may be relevant to the subjects' continued participation should be shared with them in a timely manner. On occasion, it may be necessary to re-consent the subject, in which case the process above should be followed and the subject's right to withdraw from the trial respected.

Details of all subjects consented onto the trial should be recorded on the Patient Screening and Enrolment Log, and with the subject's prior consent their General Practitioner should also be informed that they are taking part in the trial according to the local requirements. A General Practitioner Letter is provided electronically for this purpose.

6.2 Screening

During the screening period, a subject's eligibility for the trial is determined by evaluation of the exclusion and inclusion criteria. A signed informed consent (see [Section 6.1](#)) must be present before starting any screening procedures.

Subjects will undergo a medical history review as part of the screening assessment.

The parameters listed below are collected and recorded into the eCRF during the screening period. Local laboratory parameters are analysed according to standard practice e.g. plasma/serum (the same method should be used throughout the study). All screening procedures must occur within 28 days before the IMP is administered.

- Informed consent
- Demographic data (age, race, and sex)
- Inclusion/Exclusion criteria

- Medical history (current diseases including their treatment history and other relevant medical history)
- Weight
- Concomitant medications, vaccinations and interventional procedures (including herbal products) taken within 28 days prior to the signed consent or during the screening period
- ECOG performance status
- A targeted physical examination covering the major body systems (e.g. general appearance, head [ear, nose and throat], cardiovascular, eyes, respiratory, abdomen, urogenital, musculoskeletal, neurological, lymph nodes and skin)
- Vital signs (blood pressure, heart rate, body temperature and respiratory rate)
- Electrocardiography (ECG)
- Cytomegalovirus (CMV) infection status (If a subject has no symptoms, the blood test is not needed. However, if an investigator is unsure, then the test should be performed.)
- Blood sampling for
 - Human immunodeficiency virus (HIV) serology
 - Hepatitis B and C virus (immunochemical or nucleic acid test)
 - Complete blood count (CBC: white blood cells, neutrophils, lymphocytes, thrombocytes, haemoglobin)
 - Comprehensive metabolic panel (CMP): (glucose, calcium, sodium, potassium, chloride, creatinine, ALT, alkaline phosphatase (ALP), AST, creatine kinase (CK), total bilirubin, albumin)
 - Endocrine panel: cortisol, lipase, pancreas-specific amylase, thyroid stimulating hormone, parathyroid hormone (PTH), free thyroxine (T4), free triiodothyronine (T3), troponin
- Serum pregnancy test (women of child-bearing potential only)
- Tumour biopsy must be less than 6 months old from the date of consent or taken during the screening period. An archival block, if available, can be used to complement the obtained biopsy. See the Laboratory Manual for sample procurement and handling procedures.
- Brain imaging (computerized tomography (CT)). Routine diagnostic image (CT/ magnetic resonance imaging (MRI)) can be used if available. The brain scan within six weeks prior to the 1st dose is acceptable.
- AE assessment. Photographs to document visible AEs should be considered.

A subject may be re-screened if he/she fails screening but later fulfils the eligibility criteria. If the 28 day screening period has been exceeded, the subject must be re-consented to the trial and a new subject's trial number is created for the subject.

7 TRIAL ENTRY

In Part I, the screening of a subject can only be started when there is an open slot in a cohort, and it has been communicated in writing to which site the available slot has been allocated. Communications regarding the opening of upcoming cohorts and the allocation of slots to sites will be sent to all active investigators/sites to ensure transparency. The trial should not be discussed with a potential subject until a slot has been confirmed for that particular subject. Once a slot or slots has been secured by a particular subject or to the site, the signed informed consent will be obtained (see [Section 6.1](#)) and a subject number will be given to the subject(s). The eligibility of each subject will be verified by the Medical Monitor. After the eligibility check and Medical Monitor's enrolment

confirmation, any change in the subject eligibility criteria needs to be reported in the eCRF and the suitability of the subject to enter the study treatment must be carefully evaluated and confirmed by the investigator prior to Cycle 1 dosing. Other hospitals may also refer subjects to the trial, but the screening must occur at the investigative site. During Part I of the trial, confirmation that the TITE-CRM is up to date is required; if DLT information about the assigned subjects is missing from the TITE-CRM, new subjects cannot be dosed until all missing safety data is entered into the system. Once confirmed that the TITE-CRM is up to date, the initial dose of the subject may be determined. If the randomisation is applied during Part I the dose will be provided by system that handles the randomisation. Once assigned, the subject numbers for any screening failures, non-treated, non-evaluable, or discontinued subjects will not be re-used. After Part I has been completed, data has been analysed and the dose has been selected to Part II, TITE-CRM will not be used any more. However, all subjects entering the trial can be administered the IMP only after the Medical Monitor has verified the subject's eligibility.

8 TREATMENT DETAILS

8.1 Investigational Medicinal Product

The IMP is FP-1305 (bexmarilimab). Further details can be found in the latest version of the Pharmacy Manual and Investigator's Brochure.

8.1.1 Dosage Form and Composition

The IMP is clear to opalescent solution intended for intravenous application. Each 10 mL glass vial contains 250 mg of FP-1305 in histidine buffer containing stabilising excipients. The concentration of FP-1305 in the formulation is 25 mg/mL. Each vial is packed into a carton box. Further details of packaging and labelling can be found in the latest version of the Pharmacy Manual.

8.1.2 Instructions for Storage

The IMP must be stored in a secure area according to local regulations at 2-8 °C. Further details can be found in the latest version of the Pharmacy Manual.

8.1.3 Instructions for Handling the Investigational Medicinal Product

The Investigator or other designated trial personnel will maintain a log of all IMP received, dispensed, destroyed, and/or returned. Drug supplies will be inventoried and accounted throughout the trial. Detailed instructions for the handling of the IMP are given in the Pharmacy Manual.

8.2 Trial Treatment

Once the subject has been confirmed to be eligible for the trial by the Simbec-Orion Medical Monitor, the treatment period can start. The Investigator or other designated trial personnel will administer FP-1305 I.V. (peripheral or central venous line) on D1 of each cycle. The infusion rate, duration of infusion, total volume infused, and any interruption in administration will be recorded as source data and will be transferred on the appropriate eCRF page.

8.2.1 First Infusion

- The first FP-1305 infusion should be administered I.V. at an initial rate of 50 mL/h for the first 30 minutes.
- In the absence of a hypersensitivity reaction, the infusion rate may be increased gradually as per the instructions given in the Pharmacy Manual. Infusion rate will be limited based on the dosing level and volume of saline utilised.

- If a hypersensitivity reaction develops, the infusion should be temporarily stopped for up to 3 hours. Upon resolution of the subject's symptoms, the infusion can resume at one-half the rate previously associated with hypersensitivity.
- If the subject's symptoms do not resolve within 3 hours, the administration of FP-1305 should be discontinued for this cycle.
- If a second infusion reaction develops despite a reduced infusion rate, the administration of FP-1305 should be discontinued for this cycle.

All subjects in Part I dose-escalation cohorts must be closely monitored for safety for the first 24 hours after the first IMP infusion at the trial site hospital. Subjects in the dose-expansion cohorts in Part I and in Part II must be monitored for a minimum of 6 hours after the first IMP administration. However, first three subjects testing new doses or dosing frequencies in Part II should be closely monitored for safety for the first 24 h after the first IMP infusion at the trial site hospital. In Part III, all subjects must be monitored for minimum of 4 hours after the first IMP infusion. Any subject who is deemed at risk of tumour lysis syndrome or any other safety concern by the judgement of the treating investigator may be hospitalized for a longer period.

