4.1 Dose Limiting Toxicity

DLT evaluable subjects include:

- Part I: All subjects
- Part II: The first three (or six if there is one DLT in the first three) subjects in the following cohorts
 - Q3W cohorts at dose levels that have not previously been tested in Part I
 - Q2W cohorts at each new dose level for the Q2W schema
 - Q1W cohorts at each new dose level for the Q1W schema
- Part III: DLT not applicable

DLT assessment period in Part II is shorter than in Part I, justified by the safety and tolerability data collected during the trial and enabling prompt dose escalation as a part of the 3+3 design of Part II.

- Part I: 63 days (9 weeks) following the first dose of FP-1305
- Part II: 28 days (4 weeks) following the first dose of FP-1305

A DLT is defined as a drug related AE \geq Grade 3 according to NCI-CTCAE version 5.0 occurring during the DLT assessment period and related to FP-1305. The following are exceptions to the rule:

- Grade 3 infusion reactions that resolve within 8 hours from the onset of the reaction are not defined as a DLT
- Grade 3 nausea/vomiting or diarrhea for less than 72 hours with adequate antiemetic and other supportive care are not defined as a DLT
- For thrombocytopenia, haemorrhage is required to qualify grade 3 toxicity as DLT; Grade 4 thrombocytopenia is DLT regardless of haemorrhage
- For neutropenia DLT is as follows,
 - Any neutropenic fever
 - Grade 3 neutropenia persisting $>$ 5 days or Grade 4 neutropenia
- For toxicity judged to be consistent with an acute infusion-related reaction or cytokine release syndrome, DLT will be defined as follows (Sehn 2012):
 - Grade 4 drug-related AE or
 - Grade 3 drug-related AE that cannot be resolved by infusion rate reduction or interruption, or supportive care.
- An AE which, in the opinion of the Investigator, is attributed to a study subject's underlying disease will not be considered a DLT.

In addition, the following are considered DLTs (occurring during the DLT assessment period and related to FP-1305):

- Grade ≥ 2 ALT or AST increase accompanied with bilirubin elevation $>2x$ ULN if baseline value was normal; $>2 \times$ baseline if baseline value was abnormal
- Dose delay of the 2nd cycle due to drug-related toxicity of >14 days

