8.9 Management of Toxicities

All AEs should be graded according to [Section 11.3.1](#) and proper action taken based on the clinical findings and grading.

In the following, when a limit for a laboratory parameter in plasma is indicated and the local practice is to have the test in serum, the equivalent value should be considered, and vice versa.

FP-1305 should be withheld for any of the following adverse event at least possibly related to FP-1305:

- 1) Grade 2 pneumonitis (see [Section 8.9.2.1](#))
- 2) Grade 2 or 3 colitis (see [Section 8.9.2.2](#))
- 3) Grade 2 nephritis (see [Section 8.9.2.3](#))
- 4) Grade 2 liver enzyme elevations (see [Section 8.9.2.4](#))
- 5) Grade 2 or 3 endocrinopathy (see [Section 8.9.2.5](#))
- 6) Grade 2 fibrosis due to liver injury (see [Section 8.9.4](#))
- 7) Any other severe or Grade 3 treatment-related adverse reaction
- 8) Prolonged (> 2 weeks) Grade 2 or intolerable Grade 2 toxicity

FP-1305 must be permanently discontinued for any of the following adverse event at least possibly related to FP-1305:

- 1) Any life-threatening adverse reaction (excluding endocrinopathies controlled with hormone replacement therapy and/or immunosuppressants)
- 2) Grade 3 or 4 infusion reaction (see [Section 8.9.1](#))
- 3) Grade 3 or 4 pneumonitis or Grade 2 recurring pneumonitis (see treatment in [Section 8.9.2.1](#))
- 4) Grade 4 colitis (see [Section 8.9.2.2](#))
- 5) Grade 3 or 4 nephritis (see [Section 8.9.2.3](#))
- 6) Grade 3 or 4 hepatic failure (see [Section 8.9.2.4](#))
- 7) Grade 4 endocrinopathy (see [Section 8.9.2.5](#))
- 8) Grade 3 or 4 fibrosis due to liver injury (see [Section 8.9.4](#))
- 9) Inability to reduce the corticosteroid dose to 10 mg or less of prednisone or equivalent per day within 6 weeks from the initiation of the continuous corticosteroid
- 10) Persistent Grade 2 or 3 adverse reactions (excluding endocrinopathies controlled with hormone replacement therapy and/or immunosuppressants) that do not recover to Grade 0-1 within 6 weeks after the last dosing of FP-1305 and that are considered clinically significant
- 11) Any haematological or non-haematological Grade 3 treatment-related adverse reaction that recurs

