Grade 3 or 4 infusion reaction (A prolonged reaction that does not rapidly respond to symptomatic treatment, with possible recurrence of symptoms following initial improvement, hospitalization indicated for the clinical sequelae, or life-threatening requiring pressor or ventilatory support): Interrupt the infusion but maintain a vascular access with normal saline. Epinephrine should be considered depending on the severity of the reaction. Corticosteroids may be given IV or orally; oral administration is sufficient in less severe anaphylactic events. Vital sign assessment should be periodically repeated until the subject is stable. The administration of FP-1305 is permanently discontinued.

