10.4 Trial Subject Withdrawal/Discontinuation

Administration of the IMP and the subject's participation in the study must be discontinued for any of the following reasons:

- 1) Withdrawal of informed consent
- 2) In the case of any clinical AE, laboratory abnormality or illness leading to the conclusion by the investigator that participation into the trial is not the best interest of the subject
- 3) In the occurrence of toxicities as defined in [Section 8.9](#)
- 4) Pregnancy
- 5) Termination of the trial by the Sponsor
- 6) Loss of ability to freely provide informed consent
- 7) Inability to comply with protocol
- 8) Disease progression (for treatment beyond RECIST defined disease progression see [Section 8.10](#))
- 9) Dosing delays greater than the maximum allowed dosing delays as defined in [Section 8.7](#)

All trial subjects should comply with the protocol specified follow-up procedures as outlined in [Section 8.5](#). The only exception to this requirement is a withdrawal of informed consent for all trial procedures or when a subject has lost the ability to consent freely. All data collected until the withdrawal of informed consent will be analysed and included into trial data.

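### Protocol 8.2.1 and 8.2.2 manage infusion reactions without a grade limit; for Grade 3-4 reactions this is inconsistent with the mandatory permanent stop in 8.9, 8.9.1 and 10.4

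*Protocol*

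**What the plan says.** The infusion instructions are in Protocol 8.2.1 and 8.2.2. In 8.2.1 any hypersensitivity reaction leads to a pause of up to 3 hours. After that:

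- A reaction that persists ends dosing for the current cycle only: "If the subject's symptoms do not resolve within 3 hours, the administration of FP-1305 should be discontinued for this cycle".
- A second infusion reaction at the reduced rate also ends dosing for the current cycle only.
- A reaction that clears allows a restart: "Upon resolution of the subject's symptoms, the infusion can resume at one-half the rate previously associated with hypersensitivity".

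Section 8.2.2 says that subjects who develop a hypersensitivity reaction are premedicated with acetaminophen, an antihistamine and a glucocorticoid before each treatment cycle. It also carries the first-infusion guidance over to the first subsequent infusion. Neither section names a grade or refers to 8.9 or 8.9.1.

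The toxicity rules are elsewhere. Section 8.9 opens with "All AEs should be graded according to" the severity section. Its mandatory permanent-discontinuation list, for events at least possibly related to FP-1305, has as item 2 "Grade 3 or 4 infusion reaction". Section 8.9.1 describes Grade 3-4 as "A prolonged reaction that does not rapidly respond to symptomatic treatment", possibly recurring after initial improvement, or needing hospitalisation, or life-threatening. It concludes: "The administration of FP-1305 is permanently discontinued". Section 10.4, item 3, requires the drug and study participation to stop "In the occurrence of toxicities as defined in" Section 8.9.

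**The concern.** Staff at the bedside during a reaction are most likely to be working from the infusion section. That section is complete as a procedure: pause, restart or abandon, then premedicate for later cycles. Nothing in it says that the procedure ends at Grade 2, and nothing sends the reader to the rule that takes over at Grade 3.

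What is at stake is re-exposure to a first-in-human antibody after a severe reaction, either on the same day at half rate or at a later cycle under premedication. The error runs one way: following the infusion section alone can only give more drug than 8.9 allows. Section 13 says that the protocol is to be followed exactly, and for a severe reaction a site cannot act on the whole 8.2 sequence and also comply with 8.9.

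**Working it through.** No arithmetic applies. The check sets each ungraded step beside the graded rules.

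| Step in 8.2.1 / 8.2.2 | Grade 1-2 under 8.9.1 | Grade 3-4 under 8.9, 8.9.1, 10.4 |
|---|---|---|
| Restart at half rate once symptoms clear | Compatible: Grade 2 may restart at no more than 50% of the earlier rate | Direct conflict: any further dose is forbidden |
| Unresolved at 3 hours: stop for the current cycle | Compatible | Incomplete: the stop must be permanent; the cycle limit implies later dosing |
| Second reaction at reduced rate: stop for the current cycle | Compatible: infusion stopped on recurrence, prophylaxis for the next dose | Incomplete if either reaction is Grade 3-4; same implication |
| Premedicate before each treatment cycle | Compatible | Authorises no dose by itself, but assumes doses that should not occur |

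**Do the two sets of rules cover the same events?** Section 8.2.1 begins with a hypersensitivity reaction and, two bullets later, calls the next one a second infusion reaction, so it does not keep the terms apart. Section 8.8 says cytokine-release syndrome can be clinically indistinguishable from type 1 hypersensitivity and refers to 8.2.1 and 8.9.1 together for treatment.

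**Can a Grade 3-4 reaction meet the 8.2.1 triggers?** Yes.
- *Restart:* 8.9.1 includes reactions needing pressor or ventilatory support, and such a reaction could clear within the 3-hour pause. Section 4.1 also foresees Grade 3 reactions that clear within hours: "Grade 3 infusion reactions that resolve within 8 hours from the onset of the reaction are not defined as a DLT". That sentence classifies DLTs and gives no dosing permission; it is used here only to show that the case is foreseen.
- *Unresolved at 3 hours:* this overlaps the prolonged, poorly responding reaction described in 8.9.1.
- *Second reaction:* this overlaps recurrence after initial improvement, which 8.9.1 also names.

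**Does any pointer limit 8.2.1 or 8.2.2 to Grade 1-2?** No. Section 8.9.1 cites both, but only in its Grade 2 paragraph. The reference runs from the toxicity section to the infusion section and not back. It shows what was intended, but someone reading only 8.2 will not see it.

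**The case against.** The strongest reply is that a site can obey both sections on the cycle-limited stop. Ending this cycle is part of ending treatment, and 8.2.1 does not say that the next cycle will be given. That is correct. A reader might infer that the 3-hour rule on its own orders re-dosing after a severe reaction; the documents do not support that. Later dosing is implied by the cycle-limited wording together with the premedication step, and is not stated by either alone. The reply does not reach the half-rate restart. Its wording is permissive, but what it permits is exactly what 8.9 forbids.

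Second, the intended rule is recoverable. Sections 8.9 and 10.4 use *must* where 8.2.1 uses *should*, 8.9 already requires grading, and 8.9.1 links to the infusion sections only under Grade 2. This stands, and it is why the point is an inconsistency and not a missing safety rule.

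Third, the 3-hour rule has a proper use. Section 8.8 says that symptoms may be delayed for up to 24 hours, and 8.9.1 sets no time limit for Grade 2, so a reaction unresolved at 3 hours is not automatically Grade 3. This also stands, and the fix keeps the rule for Grade 1-2.

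Fourth, there are later checks. Grade 3-4 infusion reactions should reach the Sponsor within 24 hours (8.9.1). A serious event is reported within 24 hours, with follow-up stating whether the drug was continued (11.4). The next Q3W dose is normally 21 days away and follows a pre-dose evaluation. These make re-dosing at a later cycle less likely. None of them comes before a same-day restart.

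Finally, the Pharmacy Manual, which 8.2.1 and 8.2.2 cite for infusion rates, may contain a grade rule. It is not among the documents, and such a rule would not remove the inconsistency within the protocol.

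**Conclusion.** Wrong as written: an internal inconsistency in a safety rule, which should be fixed. For Grade 3-4 infusion reactions, one of the four ungraded steps (half-rate restart) directly permits what 8.9 forbids. The other three (the two cycle-limited stops and the premedication) imply later dosing that 8.9 rules out. For Grade 1-2 there is no conflict.

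The conclusion assumes that *hypersensitivity reaction* in 8.2 and *infusion reaction* in 8.9 cover the same events, as the protocol's own usage indicates, and that some sites will act on 8.2 without turning to 8.9. If 8.9 is applied, the subject is protected.

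The size cannot be given as a number. The documents report no frequency of such reactions. A reader might subtract the 3 hours in 8.2.1 from the 8 hours in 4.1 to get a window of conflict, but that difference has no meaning here. The first limit reads as running from the pause and the second runs from onset; the second is a DLT exemption; and the permanent stop in 8.9 does not depend on duration. A reader might also infer an effect on DLT counts or dose escalation. The documents do not support that either: 4.1 classifies DLTs separately from the dosing action.

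**What to change.** - In 8.2.1 and 8.2.2, limit the half-rate restart, the two cycle-limited stops and the premedication step to Grade 1-2 reactions.
- Add to both sections: *Grade 3-4 infusion reaction: do not resume; permanently discontinue FP-1305, see 8.9 and 8.9.1.*
- Require the reaction to be graded before any restart. This applies the existing grading duty in 8.9 at the moment of decision.
- Check that the Pharmacy Manual says the same.

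The cost is a few words in two sections. Design, sample size and analysis do not change. The change can go into the next amendment, with a clarification letter to sites in the meantime.
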